1.2 Rationale

1.2.1 Rationale for the Trial and Selected Subject Population

Pembrolizumab has demonstrated significant clinical activity in patients with melanoma, NSCLC, HNSCC, cHL, urothelial carcinoma, cervical cancer, esophageal cancer, gastric cancer, hepatocellular carcinoma, merkel cell carcinoma, primary mediastinal large B-cell lymphoma, renal cell carcinoma, small cell lung cancer, MSI-H/dMMR cancer, and for the treatment of adult and pediatric patients with unresectable or metastatic tumor mutational burden-high (TMB-H) [≥ 10 mutations/megabase (mut/Mb)] solid tumors, as determined by an FDA-approved test, that have progressed following prior treatment and who have no satisfactory alternative treatment options.. However, a significant proportion of these patients do not respond to or progress after anti-PD-1 therapy, highlighting the need for novel strategies to optimize the efficacy of this therapy. The TIME has emerged as a critical determinant of immune checkpoint inhibitor response, with responses correlated with an immunologically active T-cell-inflamed microenvironment.³⁸ We and others have shown that NOS induces immune dysfunction in the tumor microenvironment.⁴²⁻⁴⁴ Therefore, we hypothesize that NOS inhibition, by targeting the immunosuppressive tumor microenvironment, will reverse resistance to PD-1 blockade and enhance response rates to pembrolizumab in patients with melanoma, NSCLC, HNSCC, cHL, urothelial carcinoma, cervical cancer, esophageal cancer, gastric cancer, hepatocellular carcinoma, merkel cell carcinoma, primary mediastinal large B-cell lymphoma, renal cell carcinoma, small cell lung cancer, MSI-H/dMMR cancer or patients with unresectable or metastatic tumor mutational burden-high (TMB-H) [≥ 10 mutations/megabase (mut/Mb)] solid tumors. We will increase the number of subjects enrolled to 20 subjects to allow for Screen-Fails/withdrawals/deaths. The protocol study population will remain at 12 evaluable subjects.

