3.0 ENDPOINTS

3.1 Primary Endpoint

- The primary endpoint will be the identification of the MTD of the L-NMMA and pembrolizumab combination. DLT will be defined as any treatment-related death or any \geq Grade 3 AE (NCI CTCAE v4.03) unless there is clear alternative evidence that the AE was not caused by the trial treatment (see Section 8.0 — Statistical Considerations for a detailed list of DLTs). The DLT assessment window will be defined as the duration required to complete one full cycle of treatment with the L-NMMA and pembrolizumab combination. If treatment is delayed, the timelines for dose escalation and MTD determinations will be adjusted to allow for the completion of the DLT assessment window. Subjects will be considered evaluable for the purpose of establishing dose escalation decisions and the MTD if they satisfy one of the following criteria: receive at least one complete cycle of the L-NMMA and pembrolizumab combination and complete trial assessments without a DLT within the DLT assessment window or experience a DLT within the DLT assessment window and are withdrawn from the trial.

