The study will utilize the sequential CRM for two-dimensional dose finding method of Yuan and Yin,⁶⁷ a method based entirely on a Bayesian decision framework. The trial is designed to investigate the combination at one dose level of pembrolizumab (200 mg IV Q3W) and 3 dose levels of L-NMMA (12.5, 15.0, and 20.0 mg/kg). The starting dose will be pembrolizumab at 200 mg IV Q3W and L-NMMA at 15.0 mg/kg. The trial will be comprised of 12 subjects and will utilize a standard Bayesian model averaging CRM approach to determine the appropriate dose of L-NMMA. A cohort size of 2 will be used.

The study was designed and will be conducted using Bayesian model averaging CRM software developed by the Biostatistics Department of the University of Texas M. D. Anderson Cancer Center (<https://biostatistics.mdanderson.org/SoftwareDownload/>).^{68,69} The software assumes the probability of toxicity at dose i (π_i) is modeled as $\pi_i = p_i \times \exp(\alpha)$ where p_i is a constant and α is distributed a priori as a normal random variable with mean 0 and variance 2. The software requires the investigator to specify the prior median probability of toxicity at each of the 3 doses of L-NMMA under consideration (s_i , $i = 1, 2, 3$). The CRM model assumes that toxicity is a monotonic increasing function with dose and thus, the s_i values may not decrease as i increases. The values p_i in the probability model are selected so that $E[p_i \times \exp(\alpha)] = s_i$. After the first cohort, each successive cohort is given the dose whose posterior probability of toxicity given the data collected thus far is closest to the target toxicity (the software does not allow an untried dose to be skipped). Thus as information accumulates, the model is continually updated *posteriorly* and decisions are made on the *posterior* distribution. As a result, no data is lost and

there is the assurance that the decision to increase or decrease the dose level is consistently reassessed as more information becomes available. For a dose level to be chosen as the MTD, at least 6 subjects must have received said dose.

Table 8. L-NMMA Dose Escalation

Dose Level	L-NMMA (mg/kg)
-1	12.5
0	15.0
1	20.0

The target toxicity probability will be 0.25 to 0.30 and a maximum of 12 subjects will be treated. The first cohort of subjects will be treated at dose level 0. As an extra measure of safety, the trial will be stopped early if the lowest dose level is unacceptably toxic, formally if

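### The 6-subject minimum for naming the MTD (Section 8.0) counts subjects who received the dose and is not tied to the DLT-evaluable set of Section 3.1, so read literally it can be met with fewer than 6 evaluable subjects

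*Combined protocol and SAP*

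**What the plan says.** Section 8.0 sets the only per-dose minimum in the plan: "For a dose level to be chosen as the MTD, at least 6 subjects must have received said dose". The sentence does not mention evaluability. The same section fixes the total and the cohort size: "The target toxicity probability will be 0.25 to 0.30 and a maximum of 12 subjects will be treated" and "A cohort size of 2 will be used".

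Section 3.1 defines a narrower set, expressly for MTD decisions: "Subjects will be considered evaluable for the purpose of establishing dose escalation decisions and the MTD if they satisfy one of the following criteria". The first criterion is to "receive at least one complete cycle of the L-NMMA and pembrolizumab combination and complete trial assessments without a DLT within the DLT assessment window". The second is to "experience a DLT within the DLT assessment window and are withdrawn from the trial".

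Section 1.2.1 gives the sample size in evaluable subjects, "The protocol study population will remain at 12 evaluable subjects", and sets an enrolment allowance: "We will increase the number of subjects enrolled to 20 subjects to allow for Screen-Fails/withdrawals/deaths".

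No section says whether a dosed but non-evaluable subject is replaced, and none gives an expected rate of such subjects.

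**The concern.** Section 3.1 decides whose outcomes enter the MTD decision. Section 8.0 decides when a dose has been tried often enough to be named. They use different populations, and the wider one governs the minimum.

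The gap can be reached under the plan's own schedule. Section 5.2 gives L-NMMA on Days 1–5 and pembrolizumab on Day 5 of a 21-day cycle, and the DLT window is one full cycle. A subject who has both drugs and then leaves before the cycle ends, without a DLT, has received the dose but is not evaluable. Section 5.6 lists exits of this kind, such as withdrawn consent, intercurrent illness, noncompliance and loss to follow-up.

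At stake is the basis of the primary endpoint. A minimum of 6 is meant to ensure some toxicity experience at the named dose. A subject without a DLT outcome adds to the count but not to that experience.

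**Working it through.** **Check against the plan's own figures.** The 6 is a fixed rule with no formula behind it. The design around it can be simulated from Section 8.0: three equally weighted skeletons, normal prior with mean 0 and variance 2, cohorts of 2, at most 12 subjects, start at level 0, no skipping, and the lowest-dose stopping rule. The target was set at 0.25. The power form of the model was used, because the product form as printed is not bounded by 1 and may be a text-extraction artefact. Without the 6-subject minimum, the probability of selecting no dose in Scenarios 1–5 is 0.03, 0.10, 0.20, 0.30 and 0.77, against 0.03, 0.10, 0.20, 0.29 and 0.75 in Table 9. Numbers treated agree within about 0.3 subject. Selection by dose differs by up to about 7 points, so that part is reproduced only approximately. With the minimum enforced, the no-dose figures become 0.22, 0.37, 0.49, 0.56 and 0.85. Table 9 therefore appears to omit the minimum, which is a separate matter.

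**Six dosed subjects.** With evaluability e per subject (assumed), the chance that at least one of 6 is not evaluable is 1 − e^6:
- e = 0.95: 1 − 0.735 = 0.265
- e = 0.90: 1 − 0.531 = 0.469
- e = 0.80: 1 − 0.262 = 0.738

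**The whole design.** The same simulation was run with each subject non-evaluable at random and, because of the cap of 12 treated, no replacement (3000 runs per cell). Each cell shows: chance of declaring an MTD counting received subjects / share of those MTDs with fewer than 6 evaluable / chance of declaring an MTD counting evaluable subjects.

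| Scenario | e = 0.95 | e = 0.90 | e = 0.80 |
|---|---|---|---|
| 1 | 0.79 / 0.04 / 0.74 | 0.80 / 0.10 / 0.72 | 0.78 / 0.19 / 0.63 |
| 2 | 0.64 / 0.09 / 0.57 | 0.63 / 0.18 / 0.52 | 0.62 / 0.30 / 0.43 |
| 3 | 0.49 / 0.13 / 0.43 | 0.50 / 0.26 / 0.39 | 0.48 / 0.38 / 0.28 |
| 4 | 0.41 / 0.13 / 0.36 | 0.43 / 0.25 / 0.32 | 0.41 / 0.41 / 0.23 |
| 5 | 0.15 / 0.15 / 0.12 | 0.16 / 0.31 / 0.12 | 0.14 / 0.49 / 0.07 |

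As a share of all trials, Scenario 3 at e = 0.90 gives 0.50 × 0.26 = 0.13. The simulation standard error is about √(0.5 × 0.5 / 3000) = 0.009 for a declaration probability. It is larger for the Scenario 5 shares: with 0.16 × 3000 = 480 declared MTDs, √(0.31 × 0.69 / 480) = 0.021.

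**A limit of the simulation.** It drops subjects whether or not they had a DLT, whereas Section 3.1 keeps those who have a DLT and are withdrawn. If every DLT is kept, the chance of being non-evaluable at DLT rate p is (1 − e)(1 − p). With p = 0.40 and e = 0.90 this is 0.06 instead of 0.10, and the six-subject figure becomes 1 − 0.94^6 = 0.31 instead of 0.47. The upper ends of the ranges, which come from the more toxic scenarios, are therefore likely to be too high.

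**The two totals.** Twelve treated and 12 evaluable can both hold only if every treated subject is evaluable. That has probability e^12 = 0.54, 0.28 and 0.07 at e = 0.95, 0.90 and 0.80. To reach 12 evaluable, 12/e = 12.6, 13.3 and 15.0 subjects must be dosed on average. All three lie below 20, with about 5 to 7 places left for screen failures.

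**The case against.** The strongest reply is that Section 3.1 already settles the matter. It defines evaluability for the MTD by name, and Section 1.2.1 plans in evaluable subjects, so a careful reader would count only evaluable subjects toward the 6. As evidence of intent this stands. It does not close the gap: the 12 evaluable subjects are a trial total over three doses, and Section 8.0 states its own per-dose count in other terms.

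Several stronger readings are tempting and are not supported:
- **That the sponsor means to allow an MTD on fewer than 6 evaluable subjects.** The documents show an unlinked rule, and Section 3.1 points the other way.
- **That the 6 is the only sample-size protection.** There is also the 12-subject total, a model that pools all doses, and the lowest-dose stopping rule.
- **That 8 of 20 enrolled are expected to be dosed and lost.** The allowance includes screen failures, who are never dosed.
- **That one infusion clearly suffices to count.** A subject who leaves before Day 5 has had no pembrolizumab, so whether the combination dose was received is arguable. The gap is plain only from Day 5 onward.
- **That stand-alone binomial limits measure the harm.** With no DLTs the one-sided 95% upper limit, 1 − 0.05^(1/n), is 0.39 for n = 6 and 0.53 for n = 4, but the CRM does not select doses this way. With no DLT anywhere, 2, 4 or 6 subjects at level 0 all lead the model to recommend level 1, at targets of 0.25 and 0.30 alike.

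It is also fair to object that changing the one sentence alone could be costly. The table bears this out, and the fix has to deal with it.

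**Conclusion.** The point holds as a mismatch between a stated decision rule and the plan's own definition of who informs that decision. Read literally, a dose could be named MTD with fewer than 6 evaluable subjects. A reader might go further and infer that the plan permits this by design, but Section 3.1 does not support that.

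The size is conditional. The ranges of 4–15%, 10–31% and 19–49% rest on assumed evaluability of 95%, 90% and 80%, no replacement, a target of 0.25, the power form of the model, and non-evaluability unrelated to toxicity. The last assumption probably inflates the upper ends. If every dosed subject proves evaluable, the gap never arises. The wording should still be corrected, because it governs the primary endpoint and the plan itself expects withdrawals and deaths.

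**What to change.** Make two linked changes.

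1. In Section 8.0, reword the minimum along these lines: *at least 6 DLT-evaluable subjects (Section 3.1) must have been treated at a dose level before it can be named the MTD.*
2. Reconcile the cap of 12 treated in Section 8.0 with the 12 evaluable in Section 1.2.1: state that the 12 are evaluable subjects and that dosed non-evaluable subjects are replaced within the planned enrolment of 20.

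When making the link, check the second criterion in Section 3.1. It pairs a DLT with withdrawal, so a subject with a DLT who is not withdrawn meets neither criterion as written.

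The cost is that a dose short of 6 evaluable subjects cannot be named. If non-evaluable subjects are replaced within their cohort, the trial runs as it would at full evaluability. The simulated chance of declaring an MTD is then 0.78, 0.63, 0.52, 0.43 and 0.16 in Scenarios 1–5, close to the received-count figures in the table. The remaining price is roughly 1 to 3 extra dosed subjects on average (12/e − 12). Without replacement the first change alone is expensive: in Scenario 3 the chance falls from 0.50 to 0.39 at 90% evaluability and from 0.48 to 0.28 at 80%. The two changes should therefore be made together.

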9.0 ETHICAL CONSIDERATIONS

Compliance with laws and regulations. This study will be conducted in full conformance with the International Conference on Harmonisation E6 guideline for Good Clinical Practice and the principles of the Declaration of Helsinki, or the laws and regulations of the country in which the research is conducted, whichever affords the greater protection to the individual. The study will comply with U.S. FDA regulations and applicable local, state, and federal laws.

IRB. The protocol and informed consent form will be submitted to the IRB for review and approval. Approval of both the protocol and the consent form must be obtained before any participant is enrolled. Any amendment to the protocol will require review and approval by the IRB before the changes are implemented to the study. All changes to the consent form will be IRB approved; a determination will be made regarding whether previously consented participants need to be re-consented.

Informed Consent. The consent form will be IRB-approved and the participant will be asked to read and review the document. The investigator will explain the research study to the participant and answer any questions that may arise. All participants will receive a verbal explanation in terms suited to their comprehension of the purposes, procedures, and potential risks of the study and of their rights as research participants. Participants will have the opportunity to carefully review the written consent form and ask questions prior to signing. The participants should have the opportunity to discuss the study with their surrogates or think about it prior to agreeing to participate. The participant will sign the informed consent document prior to any procedures being done specifically for the study. The participants may withdraw consent at any time throughout the course of the trial. A copy of the informed consent document will be given to the participants for their records. The rights and welfare of the participants will be protected by emphasizing to them that the quality of their medical care will not be adversely affected if they decline to participate in this study.

Confidentiality. The Sponsor maintains confidentiality standards by coding each patient enrolled in the study through assignment of a unique patient identification number. Patient medical information obtained by this study is confidential and may be disclosed to third parties only as permitted by the informed consent form signed by the patient, unless permitted or required by law. Data generated by this study must be available for inspection upon request by representatives of the U.S. FDA and other national and local health authorities, and the IRB.

11.0 APPENDICES

11.1 Common Terminology Criteria for Adverse Events v4.03

The descriptions and grading scales found in the revised NCI CTCAE v4.03 will be utilized for AE reporting. (<http://evs.nci.nih.gov/ftp1/CTCAE/About.html>)

11.2 RECIST 1.1

RECIST version 1.1 will be used in this study for assessment of tumor response. While either CT or magnetic resonance imaging may be utilized, as per RECIST 1.1, CT is the preferred imaging technique in this trial.

Eisenhauer, EA, et al. New response evaluation criteria in solid tumors: Revised RECIST guideline (version 1.1). Eur J Cancer 2009;45:228-47.

11.3 ECOG Performance Status Scale

Grade	Description
0	Normal activity. Fully active, able to carry on all pre-disease performance without restriction.
1	Symptoms, but ambulatory. Restricted in physically strenuous activity, but ambulatory and able to carry out work of a light or sedentary nature (e.g., light housework, office work).
2	In bed <50% of the time. Ambulatory and capable of all self-care, but unable to carry out any work activities. Up and about more than 50% of waking hours.
3	In bed >50% of the time. Capable of only limited self-care, confined to bed or chair more than 50% of waking hours.
4	100% bedridden. Completely disabled. Cannot carry on any self-care. Totally confined to bed or chair.
5	Dead.
Oken MM, et al. Toxicity and response criteria of the Eastern Cooperative Oncology Group. Am J Clin Oncol 1982;5:649-55.	

11.4 New York Heart Association Functional Classifications

Class	Description
I	Patients with cardiac disease but without resulting limitations of physical activity. Ordinary physical activity does not cause undue fatigue, palpitation, dyspnea, or anginal pain.
II	Patients with cardiac disease resulting in slight limitation of physical activity. They are comfortable at rest. Ordinary physical activity results in fatigue, palpitation, dyspnea, or anginal pain.
III	Patients with cardiac disease resulting in marked limitation of physical activity. They are comfortable at rest. Less than ordinary physical activity causes fatigue, palpitation, dyspnea, or anginal pain.
IV	Patients with cardiac disease resulting in inability to carry on physical activity without discomfort. Symptoms of cardiac insufficiency or of angina syndrome may be present at rest. If any physical activity is undertaken, discomfort is increased.

11.5 Nitrate/Nitrite Drug Interactions

Drug Class	Medications
Phosphodiesterase inhibitors	sildenafil, tadalafil, vardenafil, avanafil
Nitrates	isosorbide dinitrate, isosorbide mononitrate, nitroglycerin,
Nitrites	amyl nitrite, sodium nitrite
General anesthetics	Nitrous oxide
